1.2.3. Patient Disposition

Study completion and reasons for discontinuation for all randomized patients in the double-blind phase will be summarized for each treatment group. Discontinuations by reason will be tabulated by visit for each treatment group.

Time to discontinuation due to adverse events, lack of efficacy and for any reason will be analyzed using Kaplan-Meier survival techniques; the log-rank test will be used for group comparison.

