TRADIPITANT
VP-VLY-686-3101

**A RANDOMIZED, DOUBLE-BLIND, PLACEBO-
CONTROLLED, EFFICACY STUDY OF THE NEUROKININ-1
RECEPTOR ANTAGONIST VLY-686 IN PATIENTS WITH
ATOPIC DERMATITIS**

Document Type: Clinical Study Protocol
Sponsor: Vanda Pharmaceuticals Inc.
[name]
[name]
[name]
USA
Study Product: tradipitant (VLY-686)
Protocol Number: VP-VLY-686-3101
Study Phase: III
IND Number: 122741
NCT Number: NCT03568331

Date: 12 August 2019

Status: Final

SYNOPSIS

Name of Sponsor/Company: Vanda Pharmaceuticals Inc.	
Name of Investigational Product: tradipitant (VLY-686)	
Title of Study: A Randomized, Double-Blind, Placebo-Controlled, Efficacy Study of the Neurokinin-1 Receptor Antagonist VLY-686 in Patients with Atopic Dermatitis	
Study center(s): Multicenter in North America	
Studied period: Date first patient enrolled: July 2018 Estimated study duration: 6 months	Phase of development: III
Number of patients (planned): Approximately 350 patients randomized (175 per arm, 1:1 randomization scheme), diagnosed with atopic dermatitis with treatment-resistant pruritus (i.e. pruritus duration of > 6 weeks despite the use of antihistamines or corticosteroids)	
Inclusion Criteria:	

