- To evaluate the proportion of patients with improvement of WI-NRS \geq 4-point reduction.
- To evaluate the proportion of patients with improvement on SCORAD index of at least 50%, 75% or 90% improvement.
- To evaluate the proportion of patients with improvement on the EASI of at least 50%, 75% or 90% improvement.
- To assess the efficacy of tradipitant on global measures of improvement as measured by Clinical Global Impression of Change (CGI-C) and Patient Global Impression of Change (PGI-C).
- To assess the efficacy of tradipitant on quality of life as measured by the Patient Oriented Eczema Measure (POEM), Dermatology Life Quality Index (DLQI), Healthly Days Core Module (4 questions) (HRQOL-4), Insomnia Symptom Questionnaire (ISQ) and Patient Benefit Index - Pruritus (PBI-P).
- To explore the safety and tolerability of multiple oral doses of VLY-686.

Pharmacogenomic Sub-Study:

- Identify genetic markers that correlate with response to tradipitant treatment.
- Identify genetic markers that correlate with adverse events that may occur upon treatment with tradipitant.
- To identify genetic markers that are associated with atopic dermatitis and/or pruritus and disorders/diseases associated with NK-1 receptors.
- To identify genetic markers that are associated in the metabolism, distribution, and/or excretion of tradipitant and its metabolites.

Overall Design:

This is multicenter, randomized, double-blind, placebo-controlled study to be conducted in the United States. Approximately Three Hundred and Fifty (350) patients diagnosed with atopic dermatitis, who satisfy the selection criteria for the study, will be randomized to receive either tradipitant 85 mg or matching placebo BID.

The study is divided into two phases: the pre-treatment phase and the evaluation phase. The pre-treatment phase includes a screening and a baseline visit where patients' eligibility for the study will be assessed. Washout of medications will occur during the screening phase.

The evaluation phase includes 8 weeks of randomized, double-blind, placebo-controlled treatment. In-clinic evaluations will occur at Screening, Baseline, and Weeks 2, 4, 6, and 8.

Criteria for evaluation:

Efficacy:

Efficacy assessments will include:

- Worst Itch Numerical Rating Scale (WI-NRS)
- SCORing Atopic Dermatitis (SCORAD) index
- Validated Investigator Global Assessment scale for Atopic Dermatitis (vIGA-AD)
- Eczema Area and Severity Index (EASI)

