1.2.1. General

Statistical analyses will be performed using two-sided tests.

Data will be summarized by treatment group (and by visit when applicable), with respect to demographic and baseline characteristics, efficacy variables, and safety variables.

Summary statistics will include the mean, N, standard deviation, median, minimum, and maximum values for continuous variables, and frequencies and percentages for categorical variables.

For the analyses of change from baseline, only patients with a baseline and at least one (1) post-baseline measure will be included in the analysis. Unless otherwise specified, baseline is defined as the latest non-missing observation across all the visits in the screening phase, before the active study drug begins. Endpoint will be the latest non-missing observation across all the post-baseline visits in the evaluation phase.

Low enrolling sites will be pooled for analysis and the pooling algorithm will be determined prior to breaking the blind. The goal of pooling low enrolling sites is to have a sufficient number of patients per treatment group within a site for the analysis models and for the evaluation of the treatment-by-site interaction for the primary endpoint. Unless otherwise specified, the pooled sites will only be used in the analyses where the site has an effect. The actual sites rather than the pooled sites will be specified in the data listings.

Details of the model and the analyses will be specified in the SAP. All statistical analyses will be performed using SAS®, Version 9.1.3 or higher.

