1.3.2. Secondary Efficacy Analysis

The secondary efficacy outcomes include:

- DDSS
- Itch questionnaires including diary WI-NRS, site WI-NRS and VRS
- Proportion of patients with improvement of WI-NRS \geq 4-point reduction;

- SCORAD;
- EASI;
- Proportion of patients with improvement on SCORAD index of at least 50%, 75% or 90% improvement.
- Proportion of patients with improvement on the EASI of at least 50%, 75% or 90% improvement.
- vIGA-AD;
- PGI-C;
- CGI-C;
- PBI-P;
- HRQOL-4;
- POEM;
- DLQI;
- ISQ;
- Pharmacokinetic-Pharmacodynamic correlation.

Continuous endpoints will be summarized and analyzed in a similar manner as the primary endpoint. Categorical endpoints will be analyzed by a Cochran–Mantel–Haenszel (CMH) test. Details of the analysis will be described in the SAP.

Time to event data will be analyzed using the Kaplan-Meier method, and the treatment group differences will be tested by the log-rank test. Details of the analysis will be described in the SAP.

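### Kaplan-Meier curves for discontinuation due to adverse events and due to lack of efficacy would slightly overstate the proportion leaving for each reason; cumulative incidence curves would not

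*SAP*

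**What the plan says.** SAP section 1.2.3 (Patient Disposition) plans three time-to-event analyses: "Time to discontinuation due to adverse events, lack of efficacy and for any reason will be analyzed using Kaplan-Meier survival techniques". For each, "the log-rank test will be used for group comparison". It does not say how a patient who leaves for a different reason is handled in the two by-reason analyses.

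The same section plans crude displays: "Study completion and reasons for discontinuation for all randomized patients in the double-blind phase will be summarized for each treatment group", and "Discontinuations by reason will be tabulated by visit for each treatment group".

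The only other general text on time-to-event data, in section 1.3.2, names the same method: "Time to event data will be analyzed using the Kaplan-Meier method", with the log-rank test for the treatment comparison. None of the text available mentions competing risks or cumulative incidence. Section 1.2.1 defers further detail: "Details of the model and the analyses will be specified in the SAP". That separate document is not among those available.

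Follow-up is short and fixed. The Protocol synopsis says: "The evaluation phase includes 8 weeks of randomized, double-blind, placebo-controlled treatment". The planned size is given as "Approximately 350 patients randomized (175 per arm, 1:1 randomization scheme").

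**The concern.** If a patient who stops for lack of efficacy is censored in the adverse-event analysis, Kaplan-Meier removes that patient from the risk set and lets those who remain stand in for them. The estimate then answers a hypothetical question: how many would leave for adverse events if nobody could leave for anything else, and if the reasons were independent? A reader of a disposition section wants to know how many did leave for adverse events. One minus Kaplan-Meier is never below that proportion. It is above it as soon as a competing exit precedes an event of interest.

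The stake is internal consistency of the report. With a fixed 8-week phase in which each patient either completes or leaves with a recorded reason, the proportion leaving for a reason by Week 8 is simply the crude count over the number randomized. The disposition table will show that figure, and a Kaplan-Meier curve on the same patients would show a somewhat higher one. Because the excess depends on how many leave for other reasons, it can also differ between arms when the true rates for the reason of interest are the same.

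**Working it through.** **Plan's own figures.** Section 1.2.3 gives none, and no discontinuation rate appears in the documents. The only design figures are the powers in section 1.1. They reproduce with 175 per arm: 96.2% against a stated 96% (t-test, difference 1.2, SD 3), and 90.7% against a stated 91% (Fisher's exact test, 35% against 53%). Neither depends on the discontinuation curves.

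**Assumptions.** The discontinuation rates below are assumed. Cause-specific hazards are taken as constant over 8 weeks, other exits are censored when they occur, and the curves and the table use the same patients.

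**Formula.** Let T be total discontinuation by Week 8 and c the true proportion leaving for one reason.

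- Total cumulative hazard: H = −ln(1 − T).
- Cumulative hazard for that reason: H × c/T.
- One minus Kaplan-Meier for that reason: 1 − exp(−H × c/T) = 1 − (1 − T)^(c/T).
- Excess: that value minus c.

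**Worked case.** T = 20%, adverse events 5%, lack of efficacy 8%, other 7%.

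- Adverse events: 1 − 0.80^(5/20) = 5.43%, an excess of 0.43 points.
- Lack of efficacy: 1 − 0.80^(8/20) = 8.54%, an excess of 0.54 points.

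**Range of totals.** AE = adverse events, LOE = lack of efficacy.

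| Total | True AE / LOE / other | AE curve | LOE curve | Excess AE / LOE (points) |
|---|---|---|---|---|
| 10% | 2 / 3 / 5% | 2.09% | 3.11% | 0.09 / 0.11 |
| 15% | 3 / 4 / 8% | 3.20% | 4.24% | 0.20 / 0.24 |
| 20% | 5 / 5 / 10% | 5.43% | 5.43% | 0.43 / 0.43 |
| 30% | 5 / 10 / 15% | 5.77% | 11.21% | 0.77 / 1.21 |
| 30% | 5 / 15 / 10% | 5.77% | 16.33% | 0.77 / 1.33 |
| 40% | 10 / 10 / 20% | 11.99% | 11.99% | 1.99 / 1.99 |

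In relative terms the excess runs from about 4% of the true value at 10% total discontinuation to about 20% at 40%.

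**Simulation check.** With 175 patients and 2,000 runs, the mean excess for AE / LOE was 0.43 / 0.42 points in the 5/5/10% case and 0.78 / 1.21 points in the 5/10/15% case. Both agree with the formula.

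**Difference between arms.** Assume true AE discontinuation of 5% and other reasons 7% in both arms, with LOE 15% on placebo and 5% on drug.

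- Placebo, T = 27%: 1 − 0.73^(5/27) = 5.7%.
- Drug, T = 17%: 1 − 0.83^(5/17) = 5.3%.

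The two adverse-event curves differ by about 0.3 points although the true rates are equal. For scale, the standard error of a difference between two 5% proportions with 175 per arm is √(2 × 0.05 × 0.95 / 175) = 2.3 points.

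**The case against.** There is a good case for leaving the plan alone, and much of it stands.

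- **The censoring rule is inferred.** Section 1.2.3 does not say that other exits are censored when they occur, nor that one-minus-Kaplan-Meier probabilities will be tabulated. If patients leaving for other reasons were instead kept at risk to Week 8, the estimate would equal the cumulative incidence. Section 1.2.1 leaves detail to a separate SAP. This stands as a condition on the point. It does not remove it: the method is already named, and its usual implementation produces the excess.
- **The right quantity is already reported.** The by-reason table, by visit and arm, gives nearly the same information as a cumulative incidence curve. This stands and limits the harm. It also means that the curve and the table would disagree with no stated explanation.
- **The size is small.** At 20% total discontinuation the adverse-event excess is 0.43% of 175, or about 0.75 of a patient per arm. The arm difference shown above is well within sampling error. This stands.
- **No inference changes.** With other exits censored, the log-rank test is a valid comparison of cause-specific hazards. This stands.

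A reader might infer that the adverse-event and lack-of-efficacy curves ought to add up to the any-reason curve. They would not do so under any method, because patients also leave for other reasons. The additivity failure appears only when one minus Kaplan-Meier is summed over every reason, and the plan has no curve for the remaining reasons.

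A reader might also take these curves as the trial's tolerability summary or as a supportive efficacy result. The documents do not support either. Section 1.4 bases the primary safety assessment on treatment-emergent and serious adverse events and on notable vital signs, ECGs and laboratory values. Section 1.4.1 reports adverse events leading to discontinuation as proportions. Section 1.3.2 does not list discontinuation among the secondary efficacy outcomes.

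**Conclusion.** The point holds as a minor reporting matter. On the usual reading of Kaplan-Meier by reason, the two by-reason curves are biased upward as descriptions of how many patients leave for adverse events or for lack of efficacy. At 10% to 20% total discontinuation the bias is about 0.1 to 0.5 points. It passes 1 point for the more frequent of the two reasons at 30%, and reaches about 2 points at 40%.

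These sizes rest on assumed discontinuation rates, constant hazards and censoring of other exits when they occur. The direction does not depend on the assumed rates or on constant hazards; it depends only on the censoring rule and on some competing exits coming before events of interest.

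The any-reason curve is correct as planned. The log-rank tests, the primary analysis and the power are unaffected. It would be wrong to read this as a threat to any efficacy or safety conclusion.

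**What to change.** In section 1.2.3, or in the separate SAP to which the section on general methods defers:

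1. Keep Kaplan-Meier and the log-rank test for discontinuation for any reason.
2. For discontinuation due to adverse events and due to lack of efficacy, show cumulative incidence functions (Aalen-Johansen) by arm, with all other reasons for leaving as competing events.
3. Keep the log-rank test for those two reasons. State that other exits are censored when they occur, and label it a comparison of cause-specific hazards.

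With every exit reason recorded and the same patients in both displays, the Week 8 values will then agree with the disposition table.

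The cost is a few sentences of text and a standard SAS procedure, with no new data. Section 1.2 allows changes in statistical methods before database lock to be recorded in the SAP without a protocol amendment. The downside is slightly more output to explain, since the by-reason test and the by-reason curve now describe different quantities.

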1.2.4. Demography and Other Baseline Data

Demographic data and patient characteristics at screening/baseline will be listed and summarized by treatment group for all randomized patients using descriptive statistics.

Past and current medical history will be summarized by treatment group using the system organ class (SOC) as coded using the Medical Dictionary for Regulatory Activities (MedDRA) coding dictionary.

Past medical conditions will be defined as an onset date prior to randomization (Visit 2) and resolved (not on-going) as of Visit 2. Current medical conditions, defined as an onset date on or after the date of randomization (Visit 2) or an onset date prior to randomization (Visit 2) and

unresolved (on-going) as of Visit 2, will be reported separately, but similarly to the past medical conditions. If both a past and a current (on-going) medical condition record are indicated for a condition, the condition will be presented under current medical conditions only.

1.2.5. Study Medication

The number of patients at each visit will be summarized by treatment group.

The compliance to study medication, as recorded in the CRF, will also be summarized by treatment group. The proportion of patients who are significantly noncompliant in the double-blind phase, as noted in [Section 7.3](#) of this protocol, will be summarized by treatment groups.

1.2.6. Prior/Concomitant Therapy

Any medications or therapy present before the first dose of study medication (Visit 2) will be considered as prior medications. Concomitant medications (medications present while on study medication) will be recorded throughout the study and at early discontinuation. These medications will be coded using the WHO-drug dictionary. The number of patients from the Safety Population using prior or concomitant medications will be categorized by the WHO-drug category and preferred term, and presented for each treatment group. In any given category (e.g., drug category) a patient will be counted only once.

1.3. Efficacy Data Analysis

1.3.1. Primary Outcome and Methodology

The primary efficacy outcome measure for the double-blind phase will be the mean change from baseline in worst itch score, as measured by the Numerical Rating Scale (NRS) at Week 8. The primary statistical method will be the mixed effect model repeat measurement (MMRM). A detailed description of the primary analysis model and the corresponding sensitivity analysis will be included in the SAP.

As stated previously, any changes in the statistical methods that occur prior to database lock will be documented in the SAP and will not require a protocol amendment.

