
1. Ability and acceptance to provide written informed consent; and sufficiently fluent in English to participate in the trial;2. Male and non-pregnant, non-lactating female patients aged 18 – 70 years (inclusive);
a. Note: Principal investigators are advised to enroll a patient population that reflects the demographics of the overarching United States population. Demographics in this context refer to age, sex, race, and ethnicity.3. Diagnosed with atopic dermatitis
a. $\geq 1\%$ body surface area (BSA) of AD involvement at the screening and baseline visits;b. Presence of excoriations at screening and baseline visits (i.e. SCORing Atopic Dermatitis index excoriation score > 0)c. Note: Principal investigators are advised to enroll a patient population that reflects the severity distribution of the overarching atopic dermatitis population seen in the United States population. Severity in this context refers to mild, moderate, and severe atopic dermatitis.4. Suffering from chronic pruritus with pruritus being actively present for at least 6 weeks prior to screening despite the use of antihistamines or corticosteroids;5. Worst Itch Numerical Rating Scale (WI-NRS) score ≥ 5 points at the screening and baseline visit;	

6. Daily diary reporting Worst Itch Numerical Rating Score (WI-NRS) average score for maximum itch severity ≥ 7 points between screening and baseline visits;
 - a. *Note: WI-NRS average score for maximum itch severity will be determined based on the average of the 50% worst daily NRS scores for maximum itch severity (the daily scores ranging from 0 to 10) during the screening period (between visits 1 and 2). A minimum diary compliance of 70% during the screening phase (between Visits 1 and 2) is required before randomization. For patients who do not have at least 70% diary compliance preceding the planned randomization date, randomization should be postponed until this requirement is met, but without exceeding the 45-day maximum duration for screening.*
7. Patients with Body Mass Index (BMI) of ≥ 18 and ≤ 40 kg/m^2 ($\text{BMI} = \text{weight} (\text{kg}) / [\text{height} (\text{m})]^2$);
8. Patients must agree to the following study restrictions:

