- 8. Any medical procedure requiring general anesthetic within three months of the Baseline Visit or any procedure requiring sedation within one month of the baseline visit;
- 9. Current clinically significant cardiovascular, respiratory, neurologic, hepatic, hematopoietic, renal, gastrointestinal or metabolic dysfunction unless currently controlled and stable, including (but not limited to) the following:
 - a. Uncontrolled diabetes mellitus defined as HbA1c >7%;
 - b. Positive hepatitis C antibody test (anti-HCF);
 - c. Positive hepatitis B surface antigen (HBsAg);
- 10. History (including family history) or current evidence of congenital long QT syndrome or known acquired QT interval prolongation;
- 11. History of intolerance and/or hypersensitivity to medications similar to tradipitant and its accompanying excipients;
- 12. Indication of impaired liver function (values for AST, ALT, or bilirubin > 2 times the Upper Limit of Normal (ULN));
- 13. Has a creatinine level > 1.25x ULN
- 14. Anyone affiliated with the site or sponsor and/or anyone who may consent under duress;
- 15. Any other sound medical reason as determined by the Investigator including any condition which may lead to an unfavorable risk-benefit of study participation, may interfere with study compliance or may confound study results.

Investigational product, dosage and mode of administration:

A single oral capsule of tradipitant 85 mg or matching placebo will be orally administered twice daily for a total daily dose of 170 mg.

Duration of treatment (Randomization Phase): 8 weeks

Reference therapy, dosage and mode of administration:

Placebo capsules will be provided in size and appearance identical to those containing VLY-686 and will be administered orally.

Objectives:**Primary Objective:**

- To evaluate the efficacy of VLY-686 in reducing worst itch in patients with chronic pruritus in atopic dermatitis as measured by Worst Itch Numerical Rating Scale (WI-NRS) at Week 8.

Secondary Objectives:

- To evaluate the efficacy of VLY-686 in improving disease severity in patients with atopic dermatitis as measured by the validated Investigator Global Assessment scale for Atopic Dermatitis (vIGA-AD).
- To evaluate the efficacy of VLY-686 in improving disease severity in patients with atopic dermatitis as measured by the SCORing Atopic Dermatitis (SCORAD) index and Eczema Area and Severity Index (EASI).

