1. STATISTICS

1.1. Sample Size and Accrual

To detect a 1.2 point treatment difference in worst itch score, as measured by NRS, between VLY-686 and placebo with a standard deviation (SD) of 3, a sample size of 175 patients per arm (total 350 patients) provides approximately 96% power based on a two-sided Student's T-Test with a 5% significance level. In addition, a total sample size of 350 patients (175 per arm) will also provide approximately 91% power to detect a 18% response difference, according to 35% and 53% response rates on placebo and VLY-686 respectively in the phase II study, based on a two-sided Fisher's Exact Test with a 5% significance level.

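### Does the plan need changing because it does not say whether the primary worst-itch NRS is the site score or the diary score?

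*SAP*

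**What the plan says.** The primary objective in the protocol synopsis is to reduce worst itch "as measured by Worst Itch Numerical Rating Scale (WI-NRS) at Week 8". SAP section 1.3.1 gives the primary outcome as "mean change from baseline in worst itch score, as measured by the Numerical Rating Scale (NRS) at Week 8", analysed by MMRM, and leaves the detailed model to a separate SAP. The sample size in SAP section 1.1 rests on a "1.2 point treatment difference in worst itch score, as measured by NRS, between VLY-686 and placebo with a standard deviation (SD) of 3". None of the three says whether the score comes from the clinic or the diary.

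Both sources exist. Inclusion criterion 5 needs a WI-NRS "score ≥ 5 points at the screening and baseline visit", and Table 1 schedules an NRS in the pruritus assessment at V1 to V6. Inclusion criterion 6 needs a diary "average score for maximum itch severity ≥ 7 points between screening and baseline visits", computed as the mean of the worst half of the daily scores with at least 70% diary compliance. Both of those diary rules are written for the period between Visits 1 and 2.

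SAP section 1.3.2 includes among the secondary outcomes "Itch questionnaires including diary WI-NRS, site WI-NRS and VRS", and adds: "Continuous endpoints will be summarized and analyzed in a similar manner as the primary endpoint". SAP section 1.2.1 sets a general default, open to exceptions, under which "baseline is defined as the latest non-missing observation across all the visits in the screening phase". The endpoint is defined in the same visit-based way.

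**The concern.** A primary endpoint should be identifiable from its definition, and here two candidate scores share one name. Elimination does not help, because section 1.3.2 puts both on the secondary list and analyses them much like the primary. A report could therefore carry two Week 8 itch comparisons from similar models, and a reader with only this text could not say which was the 5% test.

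The two scores are not interchangeable. They have different entry minima (5 and 7), and the diary minimum applies to a worst-half mean. If the diary were primary, the supplied text would also lack a Week 8 window, an averaging rule and a minimum number of entries, and the visit-based baseline default would suit it poorly. The SD of 3 cannot be tied to either score.

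At stake would be control of the type I error, if the choice could be made after seeing results, and the relevance of the power statement to the score actually used.

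**Working it through.** **1. The plan's own power figure.** Inputs from SAP section 1.1: n = 175 per arm, difference 1.2, SD 3, two-sided 5% t-test.

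- Standard error = 3 × √(2/175) = 0.3207
- Noncentrality = 1.2 / 0.3207 = 3.742, with 2 × 175 − 2 = 348 degrees of freedom
- Power from the noncentral t = 0.9617, or 96.2%

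The stated 96% is confirmed. The second statement (35% against 53%, Fisher's exact test, 175 per arm) gives 90.7% by full enumeration, against about 91% stated.

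**2. Does power depend much on the source?** The documents give no SD by source, so the SD is varied with the difference held at 1.2 and n at 175 per arm.

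| SD | Power |
|---|---|
| 2.5 | 99.4% |
| 3.0 | 96.2% |
| 3.45 | 90% |
| 3.5 | 89.2% |
| 4.00 | 80% |

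The SD must be 15% above the planned value (3.45/3 = 1.15) before power falls below 90%. Averaging diary days would normally work the other way. Suppose SD 3 describes a single-day score and the endpoint is a 7-day mean with between-day correlation ρ. Then SD = 3 × √((1 + 6ρ)/7). For assumed ρ of 0.5, 0.7 and 0.9 this gives SD 2.27, 2.59 and 2.87, and power 99.9%, 99.1% and 97.4%.

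**3. Type I error.** If the source is fixed before unblinding there is one test at 5%. If it were left open and the better result taken, the relevant quantity is the null probability that at least one of two correlated standard normal statistics exceeds 1.96 in absolute value. The correlation is assumed.

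| Correlation | Probability |
|---|---|
| 0 | 0.0975 |
| 0.5 | 0.0907 |
| 0.7 | 0.0835 |
| 0.9 | 0.0704 |

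Zero correlation is implausible for two ratings of the same symptom in the same patients, so the lower rows are the relevant ones, and only if the choice is made late.

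**4. The diary averaging rule.** Let W be the mean of the worst half of the entries and B the mean of the other half (even number of entries). The plain mean is (W + B)/2, so W exceeds it by (W − B)/2. For assumed gaps of 1 to 3 points that is 0.5 to 1.5 points. Using one rule at baseline and another at Week 8 would shift the change in both arms by about this amount. On its own it does not bias the difference between arms.

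**5. The 4-point response.** At the entry minima, a 4-point fall is 4/5 = 80% on the site score and 4/7 = 57% on the diary score. This concerns a secondary outcome. It is also a corner case: each patient must meet both minima, so a patient at 5 in clinic also has a diary worst-half mean of at least 7.

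**6. Which source does the text point to?**

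- SAP section 1.2.1 defines baseline and endpoint by observations at visits, which fits a clinic score.
- Table 1 schedules the NRS at every visit, and Week 8 is Day 56 with a 3-day margin either way. The same column also holds early-termination readings.
- In the inclusion criteria, the WI-NRS score without a qualifier is the visit score, and the diary version is labelled as such.
- The secondary list gives no time point for the itch questionnaires. It can cover the other visits and the other source without contradicting a Week 8 primary on one of them.

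These points lean towards the site score but do not settle it.

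**The case for a change.** The strongest reply is that section 1.3.1 defers the model and its sensitivity analysis, not the identity of the endpoint. A primary outcome should not need to be inferred, and naming its source would cost one line. The visit-based default in section 1.2.1 yields to any other specification, so it proves nothing about the source. All of that stands as a remark on clarity, and a reader holding only these documents cannot be certain.

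It does not carry further. The supplied protocol is a synopsis and schedule. The supplied SAP reads as the protocol's own statistics section: it calls itself general and points to a separate SAP for the complete methodology. Sections and appendices that it cites are not in the supplied text. A definition of the itch assessment, and any on-treatment diary rule, would naturally sit there, so their absence from the plan cannot be established. The missing diary rule matters only if the diary is primary. Taking the chosen score off the secondary list would be a matter of preference and could remove its other-visit analyses.

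**Conclusion.** The supplied text leaves the source of the primary worst-itch score unnamed, but no change to the plan follows. This is a gap that the study statistician fills from the assessment definitions and the fuller SAP before database lock. SAP section 1.2 provides for that without a protocol amendment.

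No stated figure is wrong: power is 96.2% against 96%, and 90.7% against about 91%. Power stays at or above 90% up to an SD of 3.45. No bias in the treatment difference has been shown. The type I error of 7.0% to 9.8% needs a choice of source after unblinding, which the documents do not suggest, and otherwise stays at 5%.

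The conclusion assumes that the source is fixed in writing before unblinding, as the deferral to the fuller SAP implies. The correlations, diary gaps and alternative SDs used above are assumptions, not figures from the documents.
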